## LIST OF ABBREVIATIONS

Abbreviation	Definition
accrual period	time period when patients accrue into the study that begins at the same calendar time when the CI-CDS system is implemented in all clinics at a site and ends at a pre-determined calendar time
CDS	clinical decision support
CI	cognitive impairment
CI-CDS	cognitive impairment clinical decision support system
CONSORT	Consolidated Standards of Reporting Trials
DSMB	Data Safety Monitoring Board
ED	emergency department
EHR	electronic health record
EPIC	common EHR software system used by HealthPartners and other health systems to manage patient health records
GLM	generalized linear model
H<n>	Hypothesis <number>
ICC	intraclass correlation
ICD-10	International Classification of Diseases, 10 th Revision
index visit	first visit during the accrual period at a randomized clinic at which a patient meets all intervention eligibility criteria
intervention period	time period when the CI-CDS interface is operative in intervention clinics that begins at the same time as the accrual period and ends at a set calendar time
ITT	intent to treat
LMM	linear mixed model
MC-PLUS	algorithm developed in the R61 phase to identify patients at high risk of CI diagnosis
MCI	mild cognitive impairment
Mini-Cog	brief screening tool designed to help healthcare providers identify individuals who may have cognitive impairment
MMSE	Mini-Mental State Examination
MMM	Mayo Mini Mental
MoCA	Montreal Cognitive Assessment
NIH	National Institutes of Health
observation period	time period when patient outcome data accumulate that begins at the patient index visit and ends at the end of the intervention period

Abbreviation	Definition
OR	odds ratio
PCC	primary care clinician
PI	principal investigator
ROR	relative odds ratio
RR	risk ratio
SAP	Statistical Analysis Plan
SLUMS	St. Louis University Mental Status
UC	usual care

## 1.0 INTRODUCTION

The Statistical Analysis Plan (SAP) for A Technology-Driven Intervention to Improve Early Detection and Management of Cognitive Impairment expands upon the statistical information presented in the protocol and describes all planned quantitative analyses for the primary, secondary and safety outcome measures.

The overarching aim of this study is to implement a clinical decision support (CDS) tool for identifying and managing cognitive impairment (CI) in a pragmatic clinic-randomized trial to evaluate its impact on CI detection, clinician perceptions and healthcare utilization among patients with elevated risk for CI in primary care clinics.

In the R61 phase of this study, our team developed and built the CI-CDS system that will make CI a priority to address at primary care office visits for patients with elevated risk for CI. The CI-CDS system is comprised of two interdependent processes that gather and assemble volumes of electronic health record (EHR) data to 1) offer clinicians tailored, point-of-care suggestions and tools for diagnosing and managing mild cognitive impairment (MCI) and dementia, and 2) estimate the likelihood of a future dementia diagnosis.

In this R33 phase of this study, we will conduct a pragmatic clinic-randomized trial to evaluate the effectiveness of the CI-CDS system in improving care for patients with elevated risk for CI by making it easier for clinicians to assess, diagnose, and manage cognitively impaired individuals. The study will randomize clinics to implement the CI-CDS system (CI-CDS) or to continue with usual care (UC). In the intervention clinics, the CI-CDS will use data stored in the EHR to identify patients with elevated risk for CI; assemble treatment recommendations tailored to each eligible patient's current needs; display these recommendations to primary care clinicians via the CI-CDS user interface; and store analytic data from all targeted visits. In UC clinics, the CI-CDS will run invisibly in the background to identify eligible patients, assemble tailored treatment recommendations, and store analytic data from all targeted visits, but will not display to clinicians or patients.

**The specific aims of the R33 phase of this trial are:** To evaluate the effect of the CI-CDS system on rates of CI detection, clinician confidence, and healthcare utilization costs in a pragmatic cluster-randomized trial of primary care clinics randomized to CI-CDS or UC.

**Primary Objective:** To evaluate the effect of the clinical decision support (CDS) tool for identifying and managing cognitive impairment (CI) on rates of CI detection in a pragmatic cluster-randomized trial of primary care clinics randomized to intervention (CI-CDS) or usual care (UC).

**H1:** Patients with elevated CI risk at index visits in CI-CDS compared to UC clinics will have significantly higher rates of CI detection as indicated by EHR documentation of CI diagnosis in up to 24 months of follow up.

**Secondary Objectives:** To assess the extent to which the CI-CDS system increases clinician confidence in diagnosing and managing CI, or changes in healthcare utilization costs.

**H2:** Clinicians at CI-CDS compared to UC clinics will have significantly more confidence in diagnosing and managing CI, as assessed through clinician surveys.

**H3:** Among a subset of HealthPartners-insured patients with elevated CI risk at index visits, those at CI-CDS clinics will have significantly lower healthcare utilization costs

related to emergency room and inpatient visits in the follow-up period compared to similar patients at UC clinics.

Treatment effectiveness may vary as a function of contextual factors or patient characteristics. In secondary analyses, contextual factors and patient characteristics will be assessed for the extent to which the CI-CDS system is differentially effective (i.e., treatment heterogeneity) across patient subgroups, or relatedly, whether the CI-CDS intervention can reduce pre-intervention differences in CI care across patient characteristics.

## **2.0 STUDY DESIGN AND PROCEDURES**

### **2.1 Study Design Overview**

This large, unblinded, clinic-randomized pragmatic trial will evaluate the effectiveness of the CI-CDS system in improving care for patients with elevated risk for CI by making it easier for primary care clinicians to assess, diagnose, and manage individuals with CI. The study will be conducted in at least 30 HealthPartners primary care clinics, where at least 3000 patients with elevated risk for CI are estimated to receive care.

The CI-CDS software is a system level intervention comprised of 1) a passively operating web service that gathers, analyzes and retains information pertinent to every web service call, and 2) a user interface that presents a summary of algorithm results to front end users. The web service documents every web service call made by all front-end users in all participating locations so that data pertinent to all targeted visits from all eligible and accrued patients will be identically collected and available in both treatment arms. The user interface will function as the intervention delivery vehicle and therefore be operative only in intervention locations.

Clinics will be randomized equally to the CI-CDS or UC treatment group using simple randomization. CI-CDS clinics will fully implement the CI-CDS system. In these clinics, the CI-CDS will identify patients who are at high risk for CI; use data stored in the EHR for these patients to assemble treatment recommendations tailored to the current needs of each patient; display these recommendations via the CI-CDS user interface; and store analytic data from all targeted visits. UC clinics will silently implement the CI-CDS system at the same time as CI-CDS clinics so that it operates undetectably in the background. In these clinics, the CI-CDS will identify patients at high risk for CI, assemble treatment recommendations and store analytic data from all targeted visits.

The 12-month patient accrual period will begin at the same calendar time in all clinics when the CI-CDS system is implemented. The up to 24-month intervention period will begin in all clinics at the same time as the accrual period and is the time during which the CI-CDS interface will be operative in intervention clinics.

Each patient will accrue into the study at their index visit. The index visit is the first visit during the accrual period at a randomized clinic at which a patient meets all intervention eligibility criteria. The index visit date will mark the beginning of each accrued patient's observation period. Patients will have up to 24 months of observation period, and those with an index visit near the end of the accrual period will have an approximate 12-month observation period.

Following intent-to-treat (ITT) principles, all accrued patients will be attributed to the clinic at which their index visit took place, and to the treatment group to which their clinic is randomly assigned. Patients who have an index visit, and thus have accrued into the study, may have additional visits at randomized clinics prior to the end of the intervention period. The CI-CDS system is programmed to assess intervention eligibility at all visits at all randomized clinics in both treatment groups for the duration of the intervention period, and to display tailored CI-CDS for eligible post-index visits in CI-CDS clinics only.

[figure not shown]
In addition to the primary effectiveness trial, the CI-CDS system will be implemented and evaluated in a separate, independent health care system. The replication site study design will be similar in that up to 30 primary care clinics will be randomized to a CI-CDS or UC treatment group. The CI-CDS system will be fully implemented in CI-CDS clinics and partially implemented in UC clinics (i.e., working in the background to collect data but not visible to clinicians). Patients will accrue into the study at index visits over a 6-month accrual period, with an approximate 6-month observation period for the last accrued patient, resulting in a ~12-month intervention period.

Structural differences between the effectiveness and replication sites require that processes such as randomization, outcome measurement, and analysis be implemented differently at the replication relative to the effectiveness site. Information about these processes at the replication site will be provided in a site-specific supplemental analysis plan.

## 2.2 Randomization

Simple randomization will be carried out using SAS PROC PLAN to allocate clinics equally (1:1) to the CI-CDS (intervention) or UC (control) treatment arm. Because it is common for patients to see more than one clinician in a clinic location over time, and for clinicians within a clinic location to discuss aspects of care delivery with each other, the risk of intervention contamination within clinics is rather high. Randomizing by clinic rather than by PCC or patient will minimize risk of intervention contamination.

Each accrued patient will be assigned to the clinic in which his or her index visit takes place, and as such will be assigned to the treatment group to which their clinic was randomly assigned. Post-index visits may take place in the same or different clinics or treatment groups relative to

the index visit and may or may not be eligible for the CI-CDS to offer treatment recommendations. In keeping with an ITT principle, all index and post-index visits and outcome measures for each patient will be attributed to the treatment group assignment of the clinic where the index visit took place.

The nature of the intervention prevents study personnel, clinic leaders, or primary care clinicians from being blinded to the treatment group assignment of each clinic.

## **2.3 Study Eligibility**

### **2.3.1 Primary Care Clinics**

HealthPartners leaders have agreed to enroll at least 30 primary care clinics from the Twin Cities metropolitan area into this clinic-randomized effectiveness trial. The co-PIs will collaborate with HealthPartners leaders to identify specific clinics to enroll with the intention that study clinics are representative of primary care environments at this and other health systems. Clinics will be excluded from participation for reasons such as:

- likely to close or transfer ownership during the study period;
- planned leadership or operational transitions during the study period;
- established CI workflow in place;
- resident training facility;
- involved in conflicting research;
- few patients  $\geq 65$  years of age;
- pilot location.

All potential study clinics are currently using a version of the CDS platform for non-CI-related clinical domains with high use rates.

### **2.3.2 Primary Care Clinicians**

To be study-eligible, a primary care clinician must be a family physician, general internist, or adult-care non-obstetric nurse practitioner or physician assistant working at a randomized clinic. Eligible and non-eligible primary care clinicians practicing in clinics randomized to the intervention will be able to use the CI-CDS in their care of patients. Eligible primary care clinicians will be invited to complete pre-and post-implementation surveys assessing their comfort and confidence diagnosing and managing CI, perceived barriers to providing CI care (H2), and in intervention clinics, their perceptions of the CI-CDS.

### **2.3.3 Patients**

The patient populations whose data will be included in the primary effectiveness analyses are the patients who have index visits at the CI-CDS and UC clinics during the accrual period. Patients will be automatically screened by the CI-CDS algorithms for intervention eligibility at all primary care visits at the randomized clinics during the intervention period. Patients who have a visit that meets the minimal intervention eligibility criteria during the accrual period will be considered accrued into the study.

Patients are accrued into the study upon completion of an index visit. The index visit is the first visit during the accrual period at which all of the following intervention eligibility criteria are met on the visit date:

- Primary care office visit at a randomized clinic during the accrual period, and
- Patient is age 65 or over, and
- Patient has no CI diagnosis documented in the EHR prior to the visit (ICD-10 codes F01-F03, G30, G31.0, G31.2, G31.83; or F06.7, G31.84), and
- Patient has elevated risk of CI
  - Any abnormal score on a comprehensive cognitive assessment (MoCA, MMSE, Mayo Mini Mental, or SLUMS) in the prior 18 months, or
  - MiniCog score <3 in the prior 18 months and there is no evidence of a subsequent comprehensive cognitive assessment (MoCA, MMSE, MMM, SLUMS), or
  - Risk of a dementia diagnosis in the next 3 years  $\geq 15\%$  as calculated by the algorithm developed in the R61 phase

Any of the following exclusion criteria will prevent a visit from being intervention eligible, and therefore not considered for index visit status:

- Patient has received active parenteral chemotherapy within the last year
- Patient has stage 4 or equivalent cancer diagnosis
- Patient is enrolled in hospice care or palliative care programs

All accrued patients who meet these minimal eligibility criteria, except those who have opted out of research participation, will be included in the ITT primary study analyses to maximize the generalizability of study results. As this is a pragmatic clinic-randomized trial, patients on exclusion lists will have been assessed for intervention eligibility, and the CI-CDS intervention may have been delivered during a visit to a randomized clinic. All data from each patient (e.g., outcome measures) will be attributed to the treatment group assignment of the clinic where the index visit took place.

All accrued patients, including those who have opted out of research participation, will be included in the safety analyses to ensure a complete accounting of all documented safety events.

All women and members of racial or ethnic minority groups and their subpopulations who meet the above eligibility criteria will be included in accordance with the National Institutes of Health (NIH) Policy on Inclusion of Women and Minorities as Participants in Research Involving Human Subjects.

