3.1 Inclusion Criteria

Patients are accrued into the study upon completion of an index visit. All of the following intervention eligibility criteria must be met on the visit date for the visit to be an index visit:

- Primary care office visit at a randomized clinic during the accrual period, and

Definitions

Intervention Period

- CI-CDS implementation date through a predetermined time at which the interface will be turned off in the intervention clinics

Accrual Period

- CI-CDS implementation date through a predetermined time at which no more people will be included in the analytic sample

Index Visit

- Varies by patient
- First visit during accrual period at which the CI-CDS identifies that the patient is study eligible
- Patient is accrued into study at index visit

Observation Period

- Varies by patient
- Index visit date through a predetermined time at which outcome data will no longer be accumulated

- Patient is age 65 or over, and
- Patient has no CI diagnosis documented in the EHR prior to the visit, and
- Patient has
 - Any abnormal score on a comprehensive cognitive assessment (MoCA, MMSE or SLUMS) in the prior 18 months, or
 - MiniCog score <3 in the prior 18 months and there is no evidence of a subsequent comprehensive cognitive assessment (MoCA, MMSE, SLUMS), or
 - No cognitive assessment in the past 18 months and risk of a dementia diagnosis in the next 3 years $\geq 15\%$ as calculated by the MC-PLUS algorithm developed in the R61 phase, and
- First visit during the accrual period at which all prior inclusion criteria are met.

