Step 3: Patient/Caregiver and Clinician Engagement at Primary Care Office Visits. At visits with patients with elevated CI risk or with identified CI-related care opportunities, the rooming staff receives an immediate BPA to print CDS engagement materials. Using this sequence of steps successfully implemented in previous studies, the rooming staff will print the materials from a link on the BPA and give the lay version to the patient/caregiver to review while waiting for the clinician. A professional version is provided to the clinician to review before entering the exam room. This approach has been well-liked by our clinicians to help them be prepared to engage patients in their care needs before the clinician-patient interaction.

Step 4. Online CDS for Clinicians with More Detail and Tools to Promote Efficiency. Clinicians can opt to view CDS and more detailed materials and tools online through an activity that is seamlessly integrated into the EHR and can be viewed in real time for any patient at any time they choose. Newer EHR features make it easier for the web-based application to be interactive with the end user. As the user interacts with the CDS interface, a summary is generated that captures patient CI risk or diagnosis, results of additional assessments completed, and actions recommended. This summary can then be copy and pasted into the clinician’s progress note. Our team includes very experienced EPIC programmers employed by our research institute who take full advantage of new functionality as it becomes available to make the CI-CDS interface and interactive features as efficient as possible for clinicians.

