9.2 Sample Size and Randomization

9.2.1 Treatment Assignment Procedures

Clinics will be randomized 1:1 to CI-CDS or UC using simple randomization. Randomizing by clinic rather than clinician or patient is the most effective way to minimize risk of intervention contamination. Patients tend to receive most of their care over time at a single clinic, and clinicians tend to practice at a single clinic, so it is reasonable to assert that the risk of intervention contamination across clinics is low. However, it is common for patients to see more than one clinician in a clinic location over time. Randomizing by clinician is not preferable because it would increase the number of patients with multiple visits during the intervention period who would be exposed to both treatment groups over the course of these visits. Repeated use of the CI-CDS system may alter practice patterns so that clinicians may diagnose and manage care for patients with CI in the absence of prompts provided by the CDS. Randomizing by patients is not preferable because it would result in care for UC patients that was contaminated by changes in clinician practice patterns.

Each patient will be assigned to the clinic in which his or her index visit takes place, and as such will be assigned to the treatment group to which their clinic was randomly assigned. Post-index visits may take place in the same or different clinics or treatment groups relative to the index visit and may or may not be eligible for the CI-CDS to offer treatment recommendations. In keeping with an intent-to-treat principle, all index and post-index visits and outcome measures for each patient will be attributed to the treatment group assignment of the clinic where the index visit took place.

The nature of the intervention prevents study personnel, clinic leaders or primary care clinicians from being blinded to the treatment group assignment of each clinic.

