### **3.0 ANALYSIS PLAN**

#### **3.1 Reporting and descriptive analyses**

The number of patients accrued into the study will be monitored over the course of the accrual period by treatment arm, clinic and key patient characteristics (e.g., age, reason for eligibility). The number of index visits in CI-CDS clinics when a front-end user opens the CI-CDS interface

or prints CI-CDS content will also be monitored. Anomalous accrual counts or use rates will prompt investigation to ensure proper algorithm function.

Demographic and clinical patient characteristics that were available in the EHR at or prior to the index visit will be summarized for all patients in the ITT population, overall and by treatment arm. Patient characteristics related to the risk of CI or its diagnosis (e.g., age, sex, comorbidities) that are imbalanced across treatment arms may be considered for inclusion as covariates in secondary analyses. Pre-intervention characteristics will also be used as moderators in planned heterogeneity of treatment analyses.

Intervention exposure will be quantified by counting CI-CDS eligible visits through the end of each patient's observation period, and documenting CI-CDS use at those visits. Eligibility and exposure will be calculated and summarized, overall and by treatment arm.

A flow diagram will be assembled that follows the recommendations put forth in the extended Consolidated Standards of Reporting Trials (CONSORT) statement that applies to cluster randomized trials. The CONSORT figure will summarize the number of clinics and patients screened for eligibility and reasons for ineligibility; the allocation of clinics and patients to treatment arm; the range of patients per clinic by arm; intervention exposure at index and post-index visits by arm; and analyzed sample size with reasons for exclusions by arm.

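### Cognitive tests done after go-live can decide who enters H1, and only CI-CDS clinics have the tool that offers them, so patient mix can differ by arm; one supportive analysis would check this

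*SAP*

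**What the plan says.** Accrual runs for 12 months and starts, in every clinic, when the CI-CDS system is switched on (SAP 2.1). Protocol 6.2.2 allows a patient to be screened repeatedly in that time. The first visit that qualifies is the index visit.

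SAP 2.3.3 gives three routes to elevated risk, two of which depend on test results:

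- an abnormal result on one of four named comprehensive tests, with an 18-month look-back;
- "MiniCog score <3 in the prior 18 months and there is no evidence of a subsequent comprehensive cognitive assessment";
- an MC-PLUS risk of at least 15%.

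The 18 months run back from the visit date, with no cut-off at go-live. For the third route, Protocol 3.1 adds a condition that the SAP does not have: "No cognitive assessment in the past 18 months". SAP 2.3.3 also requires "Patient has no CI diagnosis documented in the EHR prior to the visit".

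Protocol 5.1 says that the interface lets users run cognitive tests and is disabled in control clinics. Its Step 4 says that the online tool "can be viewed in real time for any patient at any time they choose". Protocol 9.2.1, explaining why clinicians are not the unit of randomisation, says "Repeated use of the CI-CDS system may alter practice patterns so that clinicians may diagnose and manage care for patients with CI" even when no prompt appears.

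SAP 3.1 monitors accrual by arm, clinic and reason for eligibility. The response it states is "Anomalous accrual counts or use rates will prompt investigation to ensure proper algorithm function".

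**The concern.** H1 compares the proportion diagnosed among accrued patients. Clinic randomisation protects that comparison if accrual depends only on things the intervention cannot change. Here, being tested is an input to accrual, and testing is something the tool is meant to make easier. Protocol 6.2.6 even counts completed cognitive assessments among the actions to be measured.

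The eligibility algorithm is identical in both arms, but that does not help if its inputs differ by arm. SAP 2.4.4 treats index characteristics as preceding possible exposure. That is true of a patient's first accrual-period visit. It need not be true of a patient whose index visit follows an earlier visit to a CI-CDS clinic after go-live.

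No H1 analysis addresses this. The covariates in SAP 3.2 are examples and do not include reason for eligibility. Under SAP 3.1, imbalances may be considered only in secondary analyses. At stake is the single comparison on which Protocol 9.5.1 rests the effectiveness conclusion.

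**Working it through.** **1. The planned detectable difference.** Inputs from Protocol 9.2.2 and SAP 6.0: 34 clinics, 100 patients each, ICC 0.04, UC rate 12%, power 0.80, two-sided alpha 0.05.

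- Design effect = 1 + (100 - 1) x 0.04 = 4.96.
- Effective sample = 3,400 / 4.96 = 685.5, or 342.7 per arm.
- Solving the pooled two-proportion power formula for 80% gives 19.81%; the plan states 19.8%. All 27 cells of Table 1 reproduce within 0.06 points.
- Detectable difference = 19.8 - 12.0 = 7.8 points.

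The power figures are sound and serve here only as a yardstick.

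**2. What the rules do to individual patients.**

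- *Eligible at the first accrual-period visit:* accrued when the algorithm runs at vitals, before the clinician acts (SAP 2.3.4). Later testing cannot remove this patient.
- *Not eligible at visit 1, then tested, abnormal, not yet diagnosed, returns within the accrual period:* accrued at visit 2. If the test would not have been done in a UC clinic, the counterpart there is not accrued by this route.
- *Not eligible at visit 1, tested and diagnosed before any qualifying visit:* excluded from H1 by the no-prior-diagnosis rule.
- *Not eligible at visit 1, tested with a normal result, later crosses 15% on MC-PLUS:* excluded under Protocol 3.1 while the test is within 18 months, but accrued under SAP 2.3.3.

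The second case adds patients to the CI-CDS arm; the third and fourth take patients away.

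**3. Size if patients are added.** Suppose no patient's own chance of diagnosis changes, the base rate is 12%, and extra patients equal to a fraction f of base accrual enter the CI-CDS arm only, with diagnosis rate d:

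shift = (0.12 + f x d) / (1 + f) - 0.12

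The shift is positive only if d exceeds 12%. The documents give d = 15.1% for MiniCog<3 (Protocol 9.2.2, SAP 6.0). All values of f and the other values of d are assumptions. With f = 0.20:

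| d | CI-CDS rate | Shift (points) | P(p<0.05), no true effect |
|---|---|---|---|
| 0% (assumed) | 0.1200/1.20 = 10.00% | -2.0 | 14% |
| 15.1% (documented) | 0.1502/1.20 = 12.52% | +0.5 | 5.5% |
| 30% (assumed) | 0.1800/1.20 = 15.00% | +3.0 | 21% |
| 40% (assumed) | 0.2000/1.20 = 16.67% | +4.7 | 42% |

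The last column counts rejection in either direction. It uses the same two-proportion test, with 342.7 effective patients in UC. For CI-CDS the clinic size becomes 120, so the design effect is 1 + 119 x 0.04 = 5.76 and the effective sample is 1,700 x 1.20 / 5.76 = 354.2.

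At d = 15.1%, even f = 0.30 gives (0.12 + 0.0453)/1.30 - 0.12 = +0.7 points. To produce the full 7.8 points at d = 40% would need f = 0.078 / (0.40 - 0.198) = 0.386, that is 39% extra accrual.

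**4. Size if patients are lost.** Suppose 10% of base accrual never enters the CI-CDS arm. If those patients' rate is 30% (assumed), the arm rate becomes (0.12 - 0.10 x 0.30)/0.90 = 10.0%, a shift of -2.0 points. If their rate is 0% (assumed), it becomes 0.12/0.90 = 13.3%, a shift of +1.3 points.

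**The case against.** The strongest reply is that the pathway is narrow. The pushed alert goes to visits with elevated risk or CI-related care opportunities, and elevated-risk patients without a CI diagnosis are already accrued. The rest depends on clinicians opening the tool unprompted or on changed habits. Protocol 5.1 describes recommendations for patients at elevated risk or with CI, and no section says that the test module is populated for an unflagged patient. The remark on practice change in Protocol 9.2.1 concerns diagnosing and managing patients with CI. The patient must then test abnormal, stay undiagnosed and return within the accrual period. All of this limits the likely size. It does not close the pathway, because access for any patient is stated and no rule dates the qualifying tests.

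It is also fair that the plan has partial safeguards. Every eligibility assessment is logged, the CONSORT figure will show reasons for ineligibility, predicted risk is an example H1 covariate, and Protocol 9.5.1 would consider imbalanced characteristics for the primary model. These give some visibility. None separates patients whose qualifying test came after go-live.

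A reader might infer that the bias must favour CI-CDS. The documents do not support that. Protocol 1.2 gives MiniCog specificity of 27-85%, so added patients may include many false positives who dilute the rate, and likely-impaired patients diagnosed before any index visit leave H1.

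A reader might also infer that normal tests enrich the CI-CDS arm by closing the MC-PLUS route. That works only under Protocol 3.1, and only for patients below 15% at their first visit who later cross it. Few patients are likely to be involved.

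**Conclusion.** The concern stands in a limited form. For patients not eligible at their first accrual-period visit, the intervention can influence later accrual, so the H1 arms can differ in mix without a true effect. Neither direction nor size can be derived from the documents.

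On the one documented rate, 15.1%, the shift is about half a point at 20% extra accrual, which is negligible beside 7.8 points. That rate is an anchor, not a ceiling: it describes all MiniCog<3 patients over 12 months before the trial, and no rate is given for patients with an abnormal comprehensive test. The +4.7 points rests on an assumed 40% rate and an assumed 20% of extra patients, and should not be read as an expected bias.

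This does not invalidate the primary analysis. It is a gap that can be checked cheaply.

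**What to change.** 1. In SAP 3.2, pre-specify a supportive H1 analysis limited to patients eligible at their first screened accrual-period visit, with qualifying tests dated before go-live. Re-derive this set from the logged eligibility assessments (SAP 2.3.4).
2. Report accrued patients per 1,000 screened aged 65 or over, by eligibility route and arm, and discuss any discrepancy between the supportive and primary results.
3. Reconcile Protocol 3.1 and SAP 2.3.3 on whether the MC-PLUS route requires that there was no cognitive assessment in the past 18 months.

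The primary analysis should remain the basis for the effectiveness conclusion, as Protocol 9.5.1 states. Requiring the two analyses to agree would add an undefined second success criterion on a smaller sample, and is not proposed.

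The cost is one extra analysis from data the platform already stores. The supportive set will be smaller and less precise, because patients who became eligible only at a later visit, or only through a test after go-live, are left out.
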